PROTOCOL AMENDMENT # 7

LCCC 1522: : Phase 2 Study of High Dose Cytarabine Followed by Pembrolizumab in Relapsed and Refractory Acute Myeloid Leukemia

AMENDMENT #7 INCOPORATES (CHECK ALL THAT APPLY)

Editorial, Administrative Changes

Scientific Changes

Therapy Changes

Eligibility Changes

The purpose of this amendment is to update the eligibility criteria to reflect that liposomal cytarabine combined with daunorubicin (CPX-351) may be considered one of the allowed types of induction therapy for front-line AML that subjects must undergo prior to enrollment on this study. This change is the result of changes in standard of care AML therapy. Also, an echocardiogram is now required as a pre-study assessment.

Additional major changes to the protocol include: subjects will be allowed to receive 2 years of pembrolizumab therapy on this clinical trial as opposed of the before allowed 1 year of therapy, subjects will be allowed to undergo allogeneic stem cell infusion after greater than 21 days have elapsed as opposed to the previously mandated 30 days, an additional correlative objective will be assessed to determine the presence of minimal residual disease after pembrolizumab therapy and dose modification and supportive care guidelines for pembrolizumab will be based on the updated package insert recommendations.

Editorial, Administrative Changes

- Removal of UNCCN to change to LCCC CPO Multicenter/LCCC Multicenter
- Added in LCCC CPO Multicenter e-mail address throughout “([contact])” as a source of contact
- Table 3- change formatting and changed title to “Dose Modifications”
- Section 6.8 assessment of safety was clarified to indicated that only subjects who receive pembrolizumab will be evaluable for safety assessments. Additional clarification was made to sections 2.4.2 and 4.6 to clarify removing subjects from study due to unacceptable AEs refers to the section of the study when subjects are receiving pembrolizumab therapy and not the induction therapy phase.

Scientific and Therapy Change

- Section 1.4.3- updated language to reflect updated IB dated 29June2018
- Section 1.7 – added correlative study goal #4 -“to assess for minimal residual disease after pembrolizumab.”
- Section 3.1.5- added “liposomal cytarabine and daunorubicin (CPX-351)”.
- Section 4.3 - Maintenance Phase- Updated –To reflect that the allogeneic stem cell infusion day 0 should occur now > **21** days after the last infusion of pembrolizumab
- Section 4.10- updated to provide clarity by bulleted points
- Section 6.1- addition of screening echocardiogram as baseline prior to treatment. As a pre-study assessment for a baseline for standard of care monitoring given risk of fluid overload in patients with AML as well as risk of myocarditis with pembrolizumab.
Section 6.2- add Transthoracic Echocardiogram as a part of the assessment
- Section 6.5- End of Treatment- Subjects are now to reach a 2 years of treatment
- Section 6.7.4 - added “Minimal Residual Disease Analysis” for clarity for Cryopreserved mononuclear cells from bone marrow aspirate and/or peripheral blood will be analyzed for minimal residual disease assays via flow cytometry, DNA or RNA PCR.
- Section 7.3.3- updated FDA Expedited Reporting requirements – to provide details on FDA safety reporting
- Section 9.2- add “Financial Disclosures” to required documents and removed (NOTE: this is required if UNC holds the IND. Otherwise, the Investigator’s signature documenting understanding of the protocol and providing commitment that this trial will be conducted according to all stipulations of the protocol is sufficient to ensure compliance) as it is no longer needed.
- Section 9.5- added paragraph to add more detail on monitoring and source data queries
Section 9.6.2 – Updated to language to refer Lineberger Comprehensive Cancer Center’s Single Subject Exceptions Policy.
- Section 9.6.3- added information on how deviation should be reported.
- Section 11.1 – Appendix A updated to reflect the updated IB for supportive care
- Section 11.2 –Appendix B updated to reflect updated IB AE

Eligibility Changes

- Section 3.1.5- Inclusion Criteria updated to include “liposomal cytarabine and daunorubicin (CPX-351)” as part of the induction therapy for front-line AML

The attached version dated June 2, 2018 incorporates the above revisions

PROTOCOL AMENDMENT # 6

LCCC 1522: : Phase 2 Study of High Dose Cytarabine Followed by Pembrolizumab in Relapsed and Refractory Acute Myeloid Leukemia

AMENDMENT #6 INCOPORATES (CHECK ALL THAT APPLY)

X Editorial
Scientific Changes
X Therapy Changes
Eligibility Changes

- 1) Section 4.2 Changed to clarify the inpatient duration to reflect institutional standards to discharge patients so that there is not a specific requirement to stay in the hospital until early recovery.
- 2) Section 4.2.1- changed the cytarabine administration to “approximately” 2 hours, per institutional guidelines
- 3) Section 6.1. Added footnote 13 to T&E calendar about three times weekly labs if patients discharged before early recovery
- 4) Section 6.1 Time and events table. Added buccal swab to be collected at screening. Those patients who did not have buccal swab collected at screening should have this sample collected at any time during follow up (clarified in footnote 12)
- 5) Sections: 6.2., 6.3.3, 6.4.1.1, 6.4.2.1: The following Section were updated to reflect the Thyroid function tests to be done: TSH, T3, and free T4.

The attached version dated November 1, 2017 incorporates the above revisions

PROTOCOL AMENDMENT # 5

LCCC 1522: Phase 2 Study of High Dose Cytarabine Followed by Pembrolizumab in Relapsed and Refractory Acute Myeloid Leukemia

AMENDMENT #5 INCORPORATES (Check all that apply):

- X Editorial
- X Scientific Changes
 - Therapy Changes
 - Eligibility Changes

This protocol is amended to update definition of disease progression for PFS secondary endpoint based on revisions to AML Leukemia Net criteria in 2017. The protocol is revised to include adverse event management language provided in a Dear Investigator Letter issued on 10 February 2017 by Merck and Co., Inc. regarding cases of Stevens-Johnson syndrome (SJS), Toxic Epidermal Necrolysis (TEN) and Immune-mediated myocarditis with pembrolizumab.

Editorial

1. Section 10 Reference #2 revised to include online reference to revised AML criteria in 2017.

Scientific

2. Updated sections 4.4.6 include supportive care guidelines for SJS, TEN and immune-mediated myocarditis.
3. Added SJS, TEN and myocarditis to adverse events associated with pembrolizumab in section 5.1.6
4. Updated section 6.9.1 to include revised definition of disease progression for PFS based on revisions to Leukemia Net criteria for AML in 2017
5. Thyroid Function tests are now required and no longer optional. Thyroid function will be monitored periodically during pembrolizumab maintenance therapy. The following sections were updated to reflect this change, Time and Events table in section 6.1 and footnote #10 to this table, and Sections 6.2, 6.3.3, 6.4.1 and 6.4.2

The attached version dated June 7, 2017 incorporates the above revisions

PROTOCOL AMENDMENT # 4

LCCC 1522: Phase 2 Study of High Dose Cytarabine Followed by Pembrolizumab in Relapsed and Refractory Acute Myeloid Leukemia

AMENDMENT #4 INCORPORATES (Check all that apply):

- X Editorial, Administrative Changes
- X Scientific Changes
- X Therapy Changes
- X Eligibility Changes

Editorial, Administrative

1. Eligibility criterion 3.1.5 was subdivided for clarity
2. Study schema in section 4.1 revised to reflect up to 2 years of maintenance pembrolizumab (instead of 1 year)
3. Minor editorial changes made to Section 4.2
4. Edit to section 4.6 duration of therapy changed from 1 year to 2 years of maintenance therapy with pembrolizumab
5. Eliminated the need to obtain ECOG PS on Day 14 in the Time and Events table (section 6.1) and assessment section 6.3.3
6. Editorial revision required to have section heading 6.4.1 for Year 1 of maintenance and the corresponding assessments as 6.4.1.1 (Day1 of each cycle) and 6.4.1.2 (After every 6th cycle) during year 1 of maintenance

Eligibility changes

1. Inclusion criterion 3.1.3 changed to ECOG PS = 0-1 (previously 0-2)

Therapy Changes

1. Increased duration of pembrolizumab maintenance therapy to 2 years (instead of 1 year) as noted in Time and Event table (section 6.1)
2. Added text to section 4.5.2 to allow for intrathecal chemotherapy on maintenance phase of the protocol as long as the subject is continuing to have a clinical response to treatment

Scientific Changes

1. Subjects receiving pembrolizumab maintenance therapy will be given the option to complete a quality of life (QOL) questionnaire. Assessment of QOL was added as an exploratory objective to section 2.3 and a corresponding endpoint was added to the section 2.4.3 Exploratory endpoints. The Promis Global Health QOL assessment has been added as Appendix 11.1 to the protocol. This assessment was also added to the Time and Events table in section 6.1, footnote #13 added to Tand E table related to this assessment. Mention of this optional assessment added to sections 6.4.1 and 6.4.2 which address maintenance therapy with pembrolizumab.

2. Exploratory Objective (2.3.3) and exploratory endpoint (2.4.3.2) were added to assess for MRD after Pembrolizumab therapy
3. Footnotes #11 and #12 to Time and Events table changed to collect additional biopsies and blood samples due to extension of maintenance therapy with pembrolizumab out to 2 years
4. Because duration of maintenance pembrolizumab extended to year 2, new treatment assessment visits added i.e., 6.4.2 Year 2 of Maintenance, section 6.4.2.1 (Day 1 of each cycle) and section 6.4.2.2 (After every 6th cycle) during year 2.
5. Sections 4.2.1 and 4.2.2 modified regarding dose reductions of cytarabine due to organ dysfunction and allowance for administration of pembrolizumab in patients who have had dose reductions of cytarabine
6. Section 4.3 Maintenance section of protocol revised to allow for 2 years of maintenance pembrolizumab, thus bone marrow biopsies after every 4 (not 3) cycles of treatment (i.e., every 12 (not 9) weeks) for the first year, and then after every 6 cycles of treatment (i.e. every 18 weeks) during years 1-2. Plus up to 34 doses (not 17) of pembrolizumab may be administered.

The attached version dated March 17, 2017 incorporates the above revisions

PROTOCOL AMENDMENT # 3

LCCC 1522: Phase 2 Study of High Dose Cytarabine Followed by Pembrolizumab in Relapsed and Refractory Acute Myeloid Leukemia

AMENDMENT #3 INCORPORATES (Check all that apply):

X Editorial, Administrative Changes

Scientific Changes

Therapy Changes

Eligibility Changes

1. A clarification was made to inclusion criterion 3.1.4 that recurrent AML will be defined by $\geq 5\%$ myeloblasts in bone marrow aspirate and/or biopsy
2. Added [name] to list of Co-investigators
3. Modified section 9.4 registration procedures to allow for the UNC Site study coordinator to review/confirm eligibility and register patients without using the network (LCCC CPO Multicenter). This process only applies to the UNC Site. Affiliate sites must register patients through the LCCC CPO Multicenter)
4. Minor editorial clarifications were added to Section 4.2, Section 6.1 (Time and Events Table Headings) and to table footnotes 2, 5, 11 and 12. Sections 6.3.4 and 6.3.5 headings were aligned with headings revised in the Table of Assessments, and finally, a cross reference was corrected in Section 7.3.4.1.
5. Corrected the heading and a footnote in the Dose Modification Table for Pembrolizumab in Section 4.3.2

The attached version dated November 9, 2016 incorporates the above revisions

PROTOCOL AMENDMENT # 2

LCCC 1522: Phase 2 Study of High Dose Cytarabine Followed by Pembrolizumab in Relapsed and Refractory Acute Myeloid Leukemia

AMENDMENT #2 INCORPORATES (Check all that apply):

- X Editorial, Administrative Changes
- X Scientific Changes
 - Therapy Changes
- X Eligibility Changes

A summary of revisions is provided as follows:

1. Updated language on required contraception for male and female participants (inclusion criteria 3.1.19 and 3.1.2) + added Section 4.2.2.1 outlining definitions of adequate contraception.
2. Revised exclusion criterion 3.2.10.
3. Revised wording in Section 4.3.2 and Table 3 in this section.
4. Revised and simplified instructions in section 4.4.6 to align with MERCK provided protocol template language.
5. Updated overdose definition in Section 5.1.10.
6. Removed LDH from Serum Chemistries in sections 6.2-6.3. LDH only included in tumor lysis labs
7. Footnote 3 of T&E calendar, specified that pembrolizumab maintenance should be given every 21 days (instead of 3 weeks) +/- 3 days to accommodate clinic schedules and holidays. This change was noted in 6.4.1 as well.
8. Revised wording in 6.4.2 to make bone marrow biopsies LESS frequent ie, Bone marrow biopsy should be performed after treatment of every 4th cycle at least 1 day prior to the next treatment cycle.
9. Footnote 11 of T&E calendar revised to indicate repeat biopsy after every 4 cycles of maintenance.
10. Updated language in 7.1.4 to include additional Merck definitions of reportable AEs
11. Revised Merck Reporting requirements in section (7.3.4) to align with MERCK provided protocol template language.
12. Section 7.3.4.1 Events of clinical interest (ECI) provides updated definitions/MERCK reporting requirements for ECI
13. Section 7.3.4.2 defines reportable pregnancy events and requirement for reporting these events to MERCK
14. Section 7.3.4.3 defines protocol-specific exceptions to SAE reporting
15. Typos corrected in Table in Section 8.2 outlining Pocock-stopping boundaries
16. Updated list of co-investigators on the title page of the protocol
17. Revised language around treatment for hyperphosphatemia in section 4.4.5

The attached version dated August 24, 2016 incorporates the above revisions

PROTOCOL AMENDMENT # 1

LCCC 1522: Phase 2 Study of High Dose Cytarabine Followed by Pembrolizumab in Relapsed and Refractory Acute Myeloid Leukemia

AMENDMENT #1 INCORPORATES (Check all that apply):

- X Editorial, Administrative Changes
 Scientific Changes
- X Therapy Changes
- X Eligibility Changes

AMENDMENT RATIONALE AND SUMMARY

Editorial Administrative changes

Minor editorial changes made throughout:

- Removed [name] as Co-Investigator
- Requirement of collection of some tissue samples has been removed (section 6.7.4)

Eligibility

1.0 BACKGROUND AND RATIONALE

1.1 Study Synopsis

This is an open-label, single arm, multicenter phase 2 study of standard salvage high dose cytarabine (HiDAC) on days 1 through 5 followed by a single dose of the humanized monoclonal antibody targeted against cell surface receptor programmed cell death-1 (PD-1), pembrolizumab, on day 14 as induction therapy in patients with relapsed and refractory acute myeloid leukemia (AML). Patients who achieve at least a partial response (PR) post-induction will continue on pembrolizumab every 3 weeks for up to 1 year of maintenance therapy. We plan to enroll 37 patients in a Simon's two-stage design.

The hypothesis of this study is that HiDAC followed by pembrolizumab will be effective in relapsed and refractory AML with a combined complete remission (CR)/CR with incomplete recovery (CRi) rate of $\geq 40\%$, superior to a historical control of 20%. We also hypothesize that the rate of unacceptable toxicity associated with HiDAC followed by pembrolizumab will not significantly exceed 20% (see section 2.4.2). Secondary endpoints include toxicity of this combination when used as induction, overall objective response rate (CR+CRi +PR) post-induction, toxicity of pembrolizumab maintenance in those patients with a response after induction, and progression-free survival (PFS), relapse-free survival (RFS) and overall survival (OS) in patients who receive maintenance pembrolizumab. We will also explore for an association between potential immune biomarkers and clinical outcomes with pembrolizumab. The overarching goals of these correlative studies are: 1) to identify and characterize mechanisms involved in T cell dysfunction in AML, 2) to identify potential predictive biomarker candidates to allow better selection of AML patients who may benefit from pembrolizumab, and 3) to identify new pathways that could be targeted to enhance the efficacy of pembrolizumab in AML.

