Recent studies have suggested that cytarabine alone has response rates 15-20% in relapsed and refractory AML patients. A randomized phase III study compared vosaroxin + cytarabine versus cytarabine alone (1 gm/m² IV daily for 5 days) in relapsed and refractory AML patients. The CR rate for patients on the vosaroxin + cytarabine arm was 30% versus 16% in patients on the cytarabine only arm.⁹ An international randomized phase III study of elacytarabine compared with physician's choice, which included high dose cytarabine, also showed CR rates of approximately 20% in the physician's choice arm.¹⁰ Additionally, a randomized phase II study by ECOG recently compared three different promising regimens for relapsed and refractory AML: Arm A: carboplatin + topotecan, Arm B: flavopiridol + cytarabine + mitoxantrone (FLAM), Arm C: Sirolimus + Mitoxantrone + Etoposide + Cytarabine. FLAM was shown to be the most effective regimen in this trial, with a CR rate of 28%, while Arm A and Arm C produced CR rates of 14% and 15%, respectively.¹¹

It is unclear whether 3 gm/m² of cytarabine is necessary and whether this dose is superior to 2 gm/m². Moreover, high doses of cytarabine (>2 gm/m²) appear to increase the risk for cerebellar toxicity, especially in older patients and those with renal disease.¹² HiDAC at doses of 1-2 gm/m² has also been evaluated in combination with other chemotherapy agents in relapsed and refractory AML patients, such as topoisomerase inhibitors (mitoxantrone and etoposide),^{3,13-15} fludarabine¹⁶, cladribine^{17,18}, and clofarabine.^{19,20} Response rates seen with these combinations range from 20-50% (median duration of response <9 months), with significant toxicities; 30-day mortality rates of these regimens range from 10-30%.

Given these data, there is a high unmet need to develop safe and effective novel therapeutic regimens for patients with refractory and relapsed AML. Investigational therapies are warranted in relapsed and refractory AML and are highly recommended over other conventional chemotherapy regimens.^{21,22}

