8.0 STATISTICAL CONSIDERATIONS

8.1 Study Design and Sample Size

This is a multi-center prospective open-label single arm phase 2 study assessing the activity of age-adjusted HiDAC (<60 years: 2 gm/m² IV Q12hours days 1-5; ≥60 years: 1.5 gm/m² IV Q12hours days 1-5) salvage induction treatment followed by pembrolizumab 200 mg IV on day 14 for relapsed or refractory AML patients.

The subjects who achieve a response (CR, CRi, or PR) to induction phase HiDAC followed by pembrolizumab 200 mg IV on day 14, as assessed by standard international European LeukemiaNet Guidelines in AML,²¹ will receive pembrolizumab 200 mg IV Q3weeks of maintenance therapy beginning 10-30 days following full hematologic recovery from induction phase. Maintenance treatment will continue until disease progression, toxicity, physician and/or patient discretion, or up to 1 year of treatment.

Simon's like two-stage design with relaxed stopping for futility will be used.⁵³ The null hypothesis that the true CR rate (CR/CRi) for HiDAC followed by pembrolizumab is 20% will be tested against a one-sided alternative hypothesis. In this study, "relaxed stopping" refers to inclusion of PR in the first stage as some of these PRs may convert to a CR during maintenance. In the first stage, 19 patients will be enrolled. If the number of patients who achieve a CR/CRi plus the number of patients with PR is equal to 4 or fewer in these 19 patients, the study will be stopped. Otherwise, 18 additional patients will be enrolled for a total of 37 patients. The null hypothesis will be rejected if 12 or more CR/CRi's are observed in 37 patients.. Assuming that the PR rate has a uniform distribution, Uniform (0, 0.05), under H₀, this design yields a type 1 error rate of at most 5% and power of at least 84% when the true CR rate for HiDAC followed by pembrolizumab is 0.4.

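### The 20% null is tested on CR+CRi, but the protocol gives neither a source for it nor any historical CR+CRi rate, and the type I error has almost no slack if 20% is a CR-only figure

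*Combined protocol and SAP*

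**What the plan says.** Section 1.1 hypothesises a combined CR/CRi rate of at least 40%, "superior to a historical control of 20" percent. Section 2.4.1 makes CR+CRi the primary endpoint. Section 8.1 states: "The null hypothesis that the true CR rate (CR/CRi) for HiDAC followed by pembrolizumab is 20% will be tested". It rejects the null at 12 or more CR/CRi among 37 patients and claims that "this design yields a type 1 error rate of at most 5% and power of at least 84" percent.

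None of these sections cites or derives the 20%. The background figures closest to it are:

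- Section 1.3, randomised phase III study: "The CR rate for patients on the vosaroxin + cytarabine arm was 30% versus 16% in patients on the cytarabine only arm".
- Section 1.3, physician's-choice arm of a second phase III study: "showed CR rates of approximately 20" percent.
- Section 1.3, HiDAC alone in primary refractory disease: 20%, labelled CR. The same series gives 44% CR overall.
- Section 1.3, summary sentence on cytarabine alone: 15-20%, labelled only as response.
- Section 1.2, salvage chemotherapy in primary refractory disease: below 20%, labelled overall response.

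Section 6.9 defines CRi separately from CR: the other CR criteria are met, but neutropenia or thrombocytopenia remains. Section 4.2 requires a marrow by day 45 even without count recovery and sets out follow-up for CRi patients, so the plan expects this category. CR alone is not among the primary or secondary endpoints in sections 2.4.1, 2.4.2 and 8.3.

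**The concern.** In a single-arm trial the historical rate is the only comparator, so it has to be on the same scale as the count tested against it. Here the count includes CRi, and nothing in the protocol shows that the 20% does. If it does not, the true no-benefit rate on the tested endpoint is 20% plus whatever CRi rate cytarabine alone produces. The trial could then reject the null, and be reported as better than history, partly because it counts a category that the benchmark left out. The 5% type I error would not apply to the question of interest, which is whether pembrolizumab adds anything.

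**Working it through.** **Inputs (section 8.1).** The null is 20% and the alternative 40%, both on CR/CRi. Stage 1 has 19 patients, and the trial stops if CR/CRi plus PR total 4 or fewer. Stage 2 adds 18. The null is rejected at 12 or more CR/CRi in 37. The PR rate is Uniform(0, 0.05) under the null.

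**Formula.** Let p be the true CR/CRi rate and q the PR rate. Let X1 ~ Bin(19, p) and X2 ~ Bin(18, p) be the CR/CRi counts in the two stages. Given X1 = x, the stage 1 PR count is Y ~ Bin(19 − x, q/(1 − p)). Then

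P(reject) = Σ over x of P(X1 = x) × P(Y ≥ 5 − x | X1 = x) × P(X2 ≥ 12 − x),

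averaged over q from 0 to 0.05.

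**Reproducing the plan.** At p = 0.20 this gives 4.85% (4.71% with q = 0, 4.96% with q = 0.05), within the stated 5%. At p = 0.40 it gives 85.1% (84.1% with q = 0), matching the stated power of at least 84%. The arithmetic in section 8.1 is correct.

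**How much slack there is.** Solving P(reject) = 5% gives p = 20.1%. The bound holds only if the CR+CRi rate without pembrolizumab benefit is about 20% or less.

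**Chance of success if pembrolizumab adds nothing, rule unchanged.** The documents give no historical CRi rate, so the increment is an assumption, shown as a range.

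| True CR+CRi on cytarabine alone | As CR 20% plus CRi | As CR 16% plus CRi | P(reject) |
|---|---|---|---|
| 16% | – | +0 | 1.0% |
| 20% | +0 | +4 | 4.85% |
| 21% | +1 | +5 | 6.7% |
| 22% | +2 | +6 | 8.9% |
| 25% | +5 | – | 18.4% |
| 26% | – | +10 | 22.4% |
| 30% | +10 | – | 41.6% |

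**Raising the null at n = 37, same stage 1 rule.** The table gives the smallest cut-off that keeps the type I error at or below 5%.

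| Null | Reject at | Type I error | Power at 40% |
|---|---|---|---|
| 22% | 13 or more | 4.6% | 76.9% |
| 25% | 15 or more | 2.7% | 53.4% |
| 30% | 17 or more | 2.9% | 28.2% |

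**The case against.** A reader might infer that the 20% was built from CR-only rates and that the null therefore omits CRi. The documents do not support that as a fact, for three reasons.

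- No section derives the 20%. The 15-20% summary in section 1.3 and the below-20% figure in section 1.2 are called response rates. If they include CRi or PR, the mismatch disappears or reverses.
- The label CR does not prove that CRi was excluded. Sections 2.1, 8.1 and 8.3 themselves use CR rate for the pooled endpoint. They say so in parentheses, which section 1.3 does not, but only the cited papers could settle the point.
- 20% is the top of the protocol's own 15-20% range. From 16%, four points of CRi still leave the type I error within 5%.

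Nor is CRi a loose category. Section 6.9 requires the other CR criteria plus independence from platelet transfusion. Section 4.2 follows CRi patients for up to 30 days and reclassifies those whose counts recover, after a repeat marrow. The benchmarks also differ in dose and population, so endpoint labelling is one uncertainty among several.

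All of this stands, and it makes the inflation conditional. The gap remains: nothing in the protocol supports 20% as a CR+CRi rate, and the plan does not commit to a comparison on the scale of the CR-labelled figures it cites.

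**Conclusion.** The concern holds in conditional form. The null is set on CR+CRi without a source and without any historical CR+CRi rate, and the design has about 0.1 percentage point of slack before the type I error passes 5%. If 20% is a CR-only rate, an assumed 1, 2, 5 or 10 points of CRi on cytarabine alone makes the false-success probability 6.7%, 8.9%, 18.4% or 41.6%. If the relevant CR rate is 16%, the null covers about 4 points of CRi; +5 gives 6.7% and +10 gives 22.4%.

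The documents do not say which case applies, so no single corrected type I error can be claimed. The larger increments are illustrations, not estimates. If the 20% is shown to include CRi, the endpoint mismatch does not arise.

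**What to change.** Keep the pooled primary test and the 12-of-37 rule. Then:

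1. State in sections 1.1 and 8.1 where the 20% comes from and whether it includes CRi. If it does, that sentence closes the point.
2. Pre-specify in section 8.3 the CR-alone rate with its 95% confidence interval, shown beside the CR-labelled benchmarks.
3. Unless the 20% is shown to include CRi, limit any claim of superiority to historical control to that like-for-like comparison. State also that the 5% type I error holds only if the CR+CRi rate without pembrolizumab is no more than 20%.

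The cost is one extra reported proportion and a few sentences. CR and CRi are already classified separately (sections 4.2 and 6.9), and section 8.3 already plans frequency tables and 95% confidence intervals, so no new data are needed. The downside is that CR alone cannot exceed CR+CRi and will usually be smaller, so the headline claim may be weaker.

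Restating the null at n = 37 is not a cheap alternative: power at 40% falls to about 77% for a 22% null and about 53% for a 25% null.
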